### **Exclusion Criteria:**

- 1)Poor oral hygiene condition.
- 2)Pregnant and lactating females.
- 3)Smokers.
- 4)Vulnerable groups (Prisoners and handicaps).

### **Justification for Exclusions:**

To reduce any confounding factors and biases that may affect the results of this study.

### **Study procedures:**

**1- Randomization and allocation concealment technique:** Patients will be randomly allocated according to predetermined computer-generated randomization using [www.Randomizer.org](http://www.Randomizer.org)

### **2- Details of the interventions, testing and follow up:**

- Group I (Customized Zirconia-Based Composite Healing Abutment):  
11 patients will receive delayed implant and a customized zirconia-based composite healing abutment placed simultaneously with implant surgery.
- Group II (Customized Conventional Composite Healing Abutment):  
11 patients will receive delayed implant and a customized conventional composite healing abutment placed simultaneously with implant surgery.

### **Study protocol and surgical steps:**

This protocol will be reviewed by the Research Ethical Committee at Faculty of Dentistry, Ain Shams University.

#### **A) Presurgical procedures:**

1) Detailed clinical examination, full history, and radiographic examination (CBCT) will be performed initially to aid in patients' selection.

2) After enrollment, all participants will sign the informed consent.

3) All participants will be subjected to periodontal phase I treatment including periodontal supra- and sub-gingival debridement and oral hygiene instructions.

#### **B) Surgical procedures:**

1) After local anesthesia administration, flap is raised, osteotomy site preparation, and implant will be placed.

2) Check the ISQ to exceed or equal 70 unit.

3) A customized Light-cured Direct Zirconia-Based Composite or A customized Light-cured Direct Conventional Composite Healing Abutment will be placed.

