**Inclusion Criteria:**
  1. Patients should be systematically free from any disease as according to Cornell Medical Index-Health Questionnaire (**Pendleton et al., 2004**).
  2. Both genders.
  3. Age from 20-50 years.
  4. Missing tooth to be restored with standard implant, with no need for additional bone and soft tissue augmentation procedures (**Beretta et al., 2019**).
  5. Implants primary stability ISQ  $\geq$  70 unites using the Osstell Mentor (**Baltayan et al., 2016**).
  6. Sound Mesial and distal neighboring teeth.
  7. At least 6 natural teeth remaining in the same arch .
  8. Mouth opening  $\geq$  30mm.
  9. Thick phenotype.

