### **2-Peri-implant sulcular fluid samples:**

Peri-implant sulcular fluid sampling will be performed at the dental implant sites after 2 months of implant placement (*Lashkarizadeh et al., 2022*).

Using standardized Periopaper paper strips. Paper strips will be placed at the entrance of the peri-implant sulcus and will be inserted to a standardized depth of 1 mm at each site regardless of the PD. In order not to affect the actual fluid volume, sampling time will also standardize as 30 s. Samples with evidence of gingival bleeding were not included. The PISF samples will then be placed in sterile, wrapped Eppendorf tubes and stored until the day of laboratory analysis (*Tözüm et al., 2007*).

**3- Blinding techniques:** Single blinding (The data analysts are unaware of the treatment the participant receives).

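### Eligibility is completed by an ISQ reading taken during surgery, but the protocol does not say whether the arm is assigned before or after it and describes no allocation concealment

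*Protocol*

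**What the plan says.** All references are to the Protocol.

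- **Inclusion Criteria, item 5** makes primary stability a condition of eligibility: "Implants primary stability ISQ" of at least "70 unites using the Osstell Mentor".
- **A) Presurgical procedures** puts enrolment and consent before surgery: "After enrollment, all participants will sign the informed consent".
- **B) Surgical procedures** gives three steps in order. Step 1: "flap is raised, osteotomy site preparation, and implant will be placed". Step 2: "Check the ISQ to exceed or equal 70 unit". Step 3: "A customized Light-cured Direct Zirconia-Based Composite or A customized Light-cured Direct Conventional Composite Healing Abutment will be placed".
- **Study procedures, item 1**, whose heading covers both randomisation and allocation concealment, says: "Patients will be randomly allocated according to predetermined computer-generated randomization using" a named website. It gives no concealment method, no holder of the list and no time of assignment.
- **Item 3, Blinding techniques**, limits blinding to one role: "The data analysts are unaware of the treatment the participant receives".
- **Sample Size Calculation** requires 18 patients (9 per group) and raises this to 22 (11 per group) for dropout during follow-up only.

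No section says how a patient with an ISQ below 70 is counted: as a screen failure, an exclusion, a replacement or a patient kept in the analysis.

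**The concern.** One eligibility criterion cannot be known when the patient is enrolled. If the arm is already assigned when ISQ is read, a patient who falls short has been randomised and is then ineligible. If the operator also knows the arm, two decisions can depend on it: whether to enrol a given patient at all, and whether to repeat, accept or reject a borderline reading. The protocol prevents neither, because it describes no concealment and does not blind the operator.

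The randomised comparison is at stake. With 11 patients per arm, one or two selective exclusions can alter the balance between groups, and no later analysis of the remaining patients can restore it. A lesser point is that ISQ failures counted among the 22 would draw on an allowance reserved for follow-up dropout.

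**Working it through.** **1. Order of events.** The time-ordered text runs: enrolment and consent, phase I periodontal treatment, implant placement, ISQ check, study abutment. Randomisation is not placed anywhere in this sequence. Two orders fit the text:

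| Assignment revealed | Patient with ISQ below 70 | Can the arm influence eligibility? |
|---|---|---|
| Before the ISQ check | Already randomised; handling not stated | Yes, if the operator knows the arm |
| After the ISQ check | Not yet randomised; screen failure | Not through the ISQ decision |

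The material cannot affect the ISQ itself, since the abutment is fitted afterwards. Bias can enter only through knowledge of the arm.

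**2. The plan's own sample size.** Inputs from Sample Size Calculation: d = 1.87, two-sided alpha 0.05, power 95%, equal groups. For the two-sample t-test, power is the probability that |T| exceeds the 97.5% point of t on n1 + n2 − 2 degrees of freedom, where T is noncentral t with noncentrality d / √(1/n1 + 1/n2).

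- 8 per group: 1.87 / √(2/8) = 3.74 on 14 df; power 93.5%.
- 9 per group: 1.87 / √(2/9) = 3.97 on 16 df; power 96.1%.

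The smallest sufficient size is 9 per group, 18 in total, as stated. Raising it to 22 allows for 4/22 = 18.2% loss.

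**3. How many ISQ losses bring power below 95%?** Suppose assignment comes first and ISQ failures are dropped from the 22.

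| Left in total | Split | Power |
|---|---|---|
| 22 | 11 vs 11 | 98.6% |
| 19 | 8 vs 11 | 96.6% |
| 18 | 9 vs 9 | 96.1% |
| 18 | 8 vs 10 | 95.9% |
| 18 | 7 vs 11 | 95.2% |
| 17 | 8 vs 9 | 94.9% |
| 17 | 7 vs 10 | 94.3% |
| 17 | 6 vs 11 | 93.1% |

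Every possible split of 18 keeps at least 95%, and the best split of 17 does not. So power falls below 95% exactly when more than 4 of the 22 are lost.

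**4. Chance of that.** The protocol gives no ISQ failure rate f, so f is an assumption. P(more than 4 of 22 fail) = 1 − Σ(k = 0 to 4) C(22, k) f^k (1 − f)^(22 − k). Expected failures are 22f. Average power is taken over the binomial distribution of losses in each arm.

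| Assumed f | Expected failures | P(power below 95%) | Average power |
|---|---|---|---|
| 5% | 1.1 | 0.4% | 98.1% |
| 10% | 2.2 | 6.2% | 97.3% |
| 20% | 4.4 | 45.7% | 94.9% |

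These are losses from ISQ alone, before any follow-up dropout.

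**5. Patients needed if assignment follows the ISQ check.** Implants placed to reach 22 randomised = 22 / (1 − f), rounded up: 23.2 → 24, 24.4 → 25 and 27.5 → 28 at 5%, 10% and 20%. The 4-patient allowance then stays free for follow-up loss.

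**The case against.** The strongest reply is that the protocol nowhere says the arm is assigned before surgery. A reader might infer it because randomisation is item 1 of the study procedures. But that numbering lists topics: item 2 covers interventions and follow-up, and item 3, blinding, comes after the text on fluid sampling. A predetermined list says how the sequence was made, not when it is applied. The two materials first appear in the surgical steps after the ISQ check, so assignment at that point would fit the text. This stands. The documents do not support saying that patients are allocated first, that the list is unconcealed, or that ISQ failures are in fact post-randomisation exclusions. They support only that the order is left open and no concealment method is described.

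A second reply is that ISQ is a device reading against a fixed cut-off, which narrows the operator's discretion. That is fair, but the decision to enrol, and whether to repeat a borderline reading, remain open to influence.

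Third, a reader might treat the chance that at least one arm falls below 9 as the chance of losing the planned power. That chance is 1 − [P(at most 2 of 11 fail)]²: 3.0%, 17.1% or 61.9% at the three assumed rates. The inference fails, because one small arm can be offset by the other: 8 vs 11, 8 vs 10 and 7 vs 11 all keep at least 95%.

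**Conclusion.** The point holds as a gap in trial conduct. Eligibility depends on an intra-operative reading, the time of assignment relative to that reading is not fixed, no concealment is described and the operator is not blinded. Together these leave a route to selection bias, whose size cannot be calculated from the documents. It operates only if the arm is revealed before the ISQ reading and the operator knows it, which the protocol neither states nor prevents.

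Power is a minor matter. Given d = 1.87, independent failures at a common rate in both arms and failures dropped from the 22, the loss is small at assumed rates of 5% or 10%. Even at 20%, where falling below 95% is nearly an even chance, average power is 94.9%. Timing and concealment of assignment are protocol matters, and the change is cheap, so it should be made.

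**What to change.** Add to Study procedures, item 1, and to B) Surgical procedures, between steps 2 and 3:

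- The list is held by an existing team member who neither recruits nor operates, with assignments in sequentially numbered, opaque, sealed envelopes.
- The next envelope is opened only after an ISQ of at least 70 is recorded and before the abutment is made.
- A patient who does not meet the criterion before opening is reported as a screen failure, is not randomised and does not count among the 22.
- Every patient whose envelope is opened is analysed in the allocated arm.

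The order of the surgical steps and the ISQ threshold are unchanged. The costs are the wording, a set of envelopes, both materials at hand for every surgery, and about 2, 3 or 6 extra patients at assumed failure rates of 5%, 10% or 20%. Envelopes do not stop someone who knows all past assignments from guessing the later ones on a fixed 11:11 list, so past assignments should not be tallied for the operator. How a low ISQ is managed clinically is for the investigators and is not judged here.

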### **Assessment:**

- Clinical assessment.
- Biochemical assessment.

### **Clinical Parameters Included:**

#### **1-Clinical evaluation of soft tissue:**

Pink Esthetic Score (PES) and The Papilla Index will be evaluated and changes between the two groups will be compared at baseline, 1,2 and 3 months (*Almadani et al., 2023*).

### **Pink esthetic Score :**

Variables	0	1	2
Papilla – M	Missing	Incomplete	Complete
Papilla – D	Missing	Incomplete	Complete
Tissue contours	Unnatural	Virtually natural	Natural
Gingival level	>2 mm	1—2 mm	<1 mm
Alveolar process	Clearly resorbed	Slightly resorbed	No difference
Coloring	Clear difference	Slight difference	No difference
Soft tissue texture	Clear difference	Slight difference	No difference

### **Papilla index :**

Description	Variables
No papilla	0
Less than half of the height	1
Half or more of the height	2
Papilla fills entire proximal space	3
Papilla is hyperplastic	4

### **2-Peri-implant sulcular fluid samples:**

Peri-implant sulcular fluid sampling will be performed at the dental implant sites after 2 months of implant placement (*Lashkarizadeh et al., 2022*).

Using standardized Periopaper paper strips. Paper strips will be placed at the entrance of the peri-implant sulcus and will be inserted to a standardized depth of 1 mm at each site regardless of the PD. In order not to affect the actual fluid volume, sampling time will also standardize as 30 s. Samples with evidence of gingival bleeding were not included. The PISF samples will then be placed in sterile, wrapped Eppendorf tubes and stored until the day of laboratory analysis (*Tözüm et al., 2007*).

**3- Blinding techniques:** Single blinding (The data analysts are unaware of the treatment the participant receives).

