### ***PICOTS Elements:***

Patient/Problem	Patients that are eligible for implant placement within inclusion criteria.
Intervention	Zirconia-based composite customized healing abutment.
Comparator	Conventional composite customized healing abutment.
Outcome	Clinical evaluation of peri-implant soft tissue changes via pink esthetic score and papilla index. Biochemical assessment of IL-1 $\beta$ level in the gingival crevicular fluid using Periopaper strip.
Time	Baseline, 1,2 and 3 months after implantation.
Setting	Faculty of Dentistry, Ain Shams University.

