### **Secondary outcome:**

Determine the impact of the customized healing abutment on the level of Interleukin-1 beta (IL-1 $\beta$ ) in the gingival crevicular fluid.

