### **Clinical Relevance:**

The result will affect the gold standard in choosing the customized healing abutment material for implant patients, regarding which one offers better peri-implant soft tissue results, healing stimulation, and less inflammatory response.

- **Hypothesis:**

Direct zirconia-based composite customized healing abutments do not have a significantly different effect on peri-implant soft tissue compared to conventional composite customized healing abutment in terms of biological properties or biocompatibility or inflammatory response.

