## **VII. Materials and Methods:**

- **Study Setting:** Faculty of Dentistry, Ain Shams University.
- **Sample Size Calculation:** A power analysis was designed to have adequate power to apply a two-sided statistical test of the null hypothesis that there is no difference would be found between different tested groups regarding pink esthetic score. By adopting alpha ( $\alpha$ ) and beta ( $\beta$ ) levels of (0.05) (i.e. power=95%) and an effect size (d) of (1.87) calculated based on the results of a previous study; the total required sample size (n) was found to be (18) cases (i.e., 9 cases per group). Sample size was increased to account for possible dropout during different follow up intervals to be (22) cases (i.e., 11 cases per group). Sample size calculation was performed using R statistical analysis software version 4.3.2 for Windows.
- **Eligibility criteria:**  

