## **IX. Statistical Analysis:**

### **Statistical methods:**

Categorical data will be represented as frequency (n) and percentage (%) and will be analyzed using chi square test. Numerical data will be explored for normality by checking the data distribution, calculating the mean and median values and using Shapiro-Wilk tests. If the data is found to be normally distributed, it will be presented as mean and standard deviation values and independent t-test will be used for the analysis. If the assumption of normality is found to be violated; the data will be presented as median and range values and will be analyzed using Mann-Whitney U test. The significance level will be set at  $p<0.05$  for all tests. Statistical analysis will be performed with R statistical analysis software version 4.3.2 for Windows.

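### Does discarding blood-contaminated sulcular fluid strips at the single 2-month sampling undermine the IL-1beta comparison?

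*Protocol*

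**What the plan says.** The Protocol's section on peri-implant sulcular fluid samples fixes one collection time: "Peri-implant sulcular fluid sampling will be performed at the dental implant sites after 2 months of implant placement". It standardises insertion depth at 1 mm and sampling time at 30 s, and then states: "Samples with evidence of gingival bleeding were not included". It speaks of strips in the plural and of each site, but gives no number of strips per implant and says nothing about repeating a bloody one.

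Under Secondary outcome, IL-1beta is the only item: "Determine the impact of the customized healing abutment on the level of Interleukin-1 beta". The Hypothesis covers effects "in terms of biological properties or biocompatibility or inflammatory response", and IL-1beta is the only inflammatory marker measured.

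The sample size paragraph under Materials and Methods sizes the trial on the pink esthetic score (PES). It needs 9 per group and goes to 11 for attrition: "Sample size was increased to account for possible dropout during different follow up intervals". For normally distributed numerical data, Statistical methods says "independent t-test will be used for the analysis", with the Mann-Whitney U test otherwise.

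The Time row of the PICOTS table reads "Baseline, 1,2 and 3 months after implantation" for all outcomes together. For PES and the Papilla Index, the clinical evaluation section says they "will be evaluated and changes between the two groups will be compared at baseline, 1,2 and 3 months".

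**The concern.** The procedure says how to sample and when to discard, but not what happens after a strip is discarded. Read literally, with one strip and no second attempt, a bloody strip means a missing IL-1beta value. No later visit is described at which to replace it, and no analysis plan can recover fluid that was never collected.

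Two things would be at stake. The first is precision: the two extra patients per group are there for dropout, so samples lost to bleeding come on top. The second is selection. Bleeding plausibly accompanies the inflammation that IL-1beta reflects, so the discarded strips could be the high ones. If one material inflames more, its worst sites would drop out more often and a true difference would shrink.

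The single Time row in PICOTS also seems to promise fluid at four visits, against one in the sampling section.

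**Working it through.** **Inputs from the Protocol.** 11 per arm; 9 per arm before dropout; two-sided alpha 0.05; d = 1.87 and 95% power, both for PES. **Assumed, because the Protocol gives no figure:** bleeding rate p of 10%, 20% or 30%; the size of the IL-1beta difference; the association of bleeding with IL-1beta.

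**1. The Protocol's own figure.** Two-sample t-test, noncentrality d·√(n/2), 2n − 2 degrees of freedom. At d = 1.87, power is 0.935 with 8 per arm and 0.961 with 9, so 9 per arm is reproduced. It concerns PES. No target is set for IL-1beta.

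**2. Detectable IL-1beta difference at 80% power, same formula.**

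| n per arm | 11 | 10 | 9 | 8 | 7 | 6 |
|---|---|---|---|---|---|---|
| SD units | 1.26 | 1.33 | 1.41 | 1.51 | 1.63 | 1.80 |

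**3. Samples lost per arm and mean power for a 1.256 SD difference.** Expected loss with one strip is 11p. With one repeat, the chance that both strips are bloody is p² + ρp(1 − p), where ρ is the within-implant correlation of bleeding. Power is averaged over binomial losses in both arms, with equal bleeding and no link to IL-1beta. With no losses it is 80%.

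| p | Lost, one strip | Power, one strip | Lost, one repeat (ρ = 0 to 0.5) | Power, one repeat (ρ = 0 to 0.5) |
|---|---|---|---|---|
| 10% | 1.1 | 74.8% | 0.11 to 0.61 | 79.5% to 77.2% |
| 20% | 2.2 | 68.6% | 0.44 to 1.32 | 78.0% to 73.6% |
| 30% | 3.3 | 61.3% | 0.99 to 2.15 | 75.3% to 68.9% |

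If dropout also takes 2 per arm, one strip leaves 9 × 0.9 = 8.1 at 10% and 9 × 0.7 = 6.3 at 30%. About 1.51 to 1.80 SD is then detectable.

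**4. Dependence on the chosen effect.** The 1.256 SD is simply what gives 80% power at 11 per arm. One strip, with bleeding at 0, 10, 20 and 30%:
- true difference 0.5 SD: power 20, 18, 17 and 15%;
- true difference 1.87 SD (the PES figure): 98.6, 97, 95 and 91%.

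For a modest effect the comparison is weak with or without the rule. For a very large one it survives the rule.

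**5. Selection.** Model: P(bleed) = logistic(a + b·x), with x the standardised log IL-1beta, mean 0 in control and −d in the zirconia arm, and a set to give the control bleeding rate. Take d = 0.5 to 1.0 and b = 1 to 2 (moderate to strong association).

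| Control bleeding | Shrinkage, raw difference | Shrinkage relative to within-arm SD |
|---|---|---|
| 10% | 5–13% | 3–7% |
| 20% | 9–21% | 5–11% |
| 30% | 12–26% | 6–14% |

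Example at 10%, d = 0.5, b = 2: the raw difference is 0.435, and 1 − 0.435/0.5 = 13%. Divided by the SD after exclusion it is 0.467, and 1 − 0.467/0.5 = 7%. The second scale is smaller because discarding high values also narrows the spread, and it is the scale the t-test uses. With b = 0 the shrinkage is zero.

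If the arms have equal IL-1beta but bleed at 10% and 20%, the false difference is at most 0.12 SD (b = 2). The standard error is √(2/11) = 0.43 SD.

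**6. Timing.** The PICOTS row is a summary line for the whole trial. The clinical and fluid sections each give their own times, and these do not conflict with each other.

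**The case for a change.** The strongest case for a change is that this is chairside collection. A missing-data rule in an analysis plan comes too late for fluid that was not taken. If each strip bleeds with probability 10%, the chance of losing at least one of 22 is 1 − 0.9²² = 90%, so some loss is likely on the one-strip reading. A sentence on strip number and repeats would cost almost nothing, and step 3 shows that a repeat recovers most of the power.

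The collection point stands, and such a sentence would do no harm. But the argument needs a reading the text does not state. The plural strips, the reference to each site and the exclusion of samples rather than patients all leave room for another strip, and taking one is what a sampler would naturally do. The section also cites published methods for the procedure.

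A repeat strip is no clean cure either. It restores numbers but may favour the less inflamed aspect of the implant, so selection remains. Scoring patients without a clean strip as worst rank could over-penalise bleeding caused by inserting the strip. Reporting exclusions by arm is useful, but that is analysis-plan matter. Nor does falling below 9 usable samples breach anything, since 9 was derived for PES.

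**Conclusion.** No change to the plan is needed. The exclusion rule is right, and the unstated strip count and repeat are operating details that samplers can settle sensibly. The difference between the PICOTS Time row and the sampling section is clerical, because the outcome-specific sections explain it.

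The size rests on assumed bleeding rates and, at worst, on a one-strip, no-repeat reading. The 10% case may be the more likely one, because poor oral hygiene and smoking are exclusions and every participant receives debridement. It costs about one sample per arm and about 5 points of power at 1.26 SD. A rate of 30% with no repeat would cost more, about 19 points (80% to 61%), but nothing in the Protocol points to that rate or requires that reading. The distortion from selection is small beside the sampling error. The effect is confined to a secondary outcome with no stated precision target, and the primary outcome and its sample size are untouched.
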